### **3.6.2. Exclusion Criteria**

Subjects meeting ANY of the following criteria will be excluded from the clinical trial:

1. No Light Perception vision at screening exam in study eye.
2. Pre-phthisis eyes as per Investigator's assessment in study eye.
3. History of severe non-proliferative or proliferative diabetic retinopathy
4. History of significant intraocular inflammatory disease requiring the use of systemic anti-inflammatory medication or an intraocular anti-inflammatory medication
5. History of severe dry eye or other significant corneal disease
6. History of incisional glaucoma surgery or ciliary body destructive procedures
7. Other planned eye surgery during the course of the trial (including subjects with a diagnosis of bilateral detachments)
8. Participation in a clinical trial with an investigational medicinal product or investigational device within 90 days of subject enrollment
9. Any clinically significant laboratory test abnormalities or a history of any other systemic or ophthalmic condition, or circumstances which, in the opinion of the Investigator, could

compromise the subject's ability to comply with the protocol or that could compromise the subject's safety or the interpretation of the clinical trial results

10. History of more than 6 retinal detachments
11. Hypersensitivity to Methotrexate medication
12. Have previously received Methotrexate intravitreally at any time or plan to receive intravitreal methotrexate during the study period, or received, or systemic Methotrexate administration within 3 months of Screening visit.
13. Patients who might need to use Methotrexate for other medical conditions during the study period.

### **3.7. Strategies for Recruitment and Retention**

Subjects will be recruited directly from the investigative sites' patient population or will be referred for treatment by other physicians. Once enrolled, subjects will be provided with the visit schedule and reminders from the clinical trial staff in advance of their visits to assist with compliance to the schedule of events for the clinical trial.

Subjects who discontinue early from investigational product treatment will complete the end-of-study visit (Week 24) at time of discontinuation. The Sponsor and Investigator will make all efforts to retain all subjects in the clinical trial until the end-of-study visit (Week 24) and to follow-up with early discontinued subjects for safety purposes.

## **4. SUBJECT DISPOSITION**

### **4.1. Completed Subjects**

A completed subject is one who has not been discontinued from the clinical trial.

### **4.2. Discontinued Subjects**

Subjects may be discontinued prior to their completion of the clinical trial due to:

- Subject request/withdrawal
- AEs
- Positive pregnancy results
- Protocol violations
- Administrative reasons (e.g., inability to continue, lost to follow-up)
- Sponsor termination of the clinical trial
- Any sound medical reason, as determined by the investigator
- Others

Notification of a subject discontinuation and the reason for discontinuation will be made to the Sponsor or designee and will be clearly documented on the eCRF. Subjects who are discontinued from the clinical trial will not be replaced.

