## **3. INVESTIGATIONAL PLAN**

### **3.1. Overall Clinical Trial Design and Plan**

A Phase 3, multicenter, adaptive clinical trial comprised of approximately 100 evaluable eyes in Part 1 (Part 2 sample size will be determined after analysis of Part 1) at high-risk for recurrent retinal detachment due to PVR, or with OGI that may or may not have PVR.

- Subjects in the **Control cohort** (Part 1a only) will receive Standard Procedures only (defined in Section 7).
- Subjects in the **Intervention cohort** (Part 1a and 1b) will receive Standard Procedures and repeated intravitreal injections of ADX-2191 at a dose of 400 µg/0.05 mL for 16 weeks (Figure 1).

In Part 1a of the GUARD Study (prior to activation of Protocol Version 5.0, dated May 5 2021), eligible subjects will be randomized 1:1 intraoperatively to either the **Control** or **Intervention** cohort. Subjects in the **Control** cohort will receive Standard Procedures only. In Part 1b of this study (after activation of Protocol Version 5.0, dated May 5 2021), eligible subjects will no longer be randomized and all enrolled subjects will be placed in the **Intervention** Cohort. Subjects in the Intervention cohort will receive Standard Procedures and intravitreal ADX-2191 injections (Figure 1).

In Part 1a, stratification was used to balance treatment assignments within key subgroups. Subjects are to be stratified by clinical presentation (recurrent retinal detachment vs. OGI) and number of recurrent retinal detachments (>3 vs. ≤3).

Subjects enrolled in Part 1 will not be eligible to participate in Part 2 nor will they be eligible to be enrolled again during Part 1.

Clinical trial procedures to be conducted in Part 1 and Part 2 are outlined in the Schedule of Assessments (Table 1).

For Part 1, approximately 100 evaluable eyes must complete the 24-week clinical trial. Up to 50 additional subjects may be recruited to achieve the minimum number of evaluable subjects.

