#### **4.3. Subject Withdrawal**

If intraoperative complete retinal reattachment is not achieved, subjects will not complete enrollment. These subjects will be dropped from enrollment and will be noted as screen failures.

Subjects who have retinal detachment within 1-week post-operatively will be deemed to have failed Day 0 (day of surgery) and will be removed from the efficacy analysis. These will be considered “dropped” subjects. Subjects receiving investigational product during this period will continue to be followed for safety.

Subjects will be removed from the clinical trial if they develop infectious endophthalmitis and/or no light perception vision.

Subjects may also be removed at the discretion of the principal investigator or at the wishes of the subject himself/herself.

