## **9. STATISTICS HYPOTHESES AND METHODS OF ANALYSES**

### **9.1. Clinical Trial Populations**

#### **9.1.1. Intent-to-Treat (ITT)**

The Intent-to-Treat (ITT) population consists of all subjects who were randomized. All data will be included, and no subjects will be excluded because of protocol violations. All data will be included, and no subjects will be excluded because of protocol violations; subjects who have retinal detachment within 1-week post-operatively who will be deemed to have failed Day 0 (surgery) and will be removed from the efficacy analysis as per protocol per Section 2.2.1.

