### **9.4.2. General Imputation Methods**

Every attempt will be made to capture all clinical trial data. The method on how to handle the complete and/or partial missing data in the adverse events and medications will be addressed in these individual analysis sections of the SAP. No imputation method will be applied on recurrent retinal detachment data.

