#### **9.4.5. Primary Efficacy Analyses**

The primary efficacy variable of recurrent of retinal detachments (defined in Section 3.6) due to PVR requiring re-operation within six months from enrollment will be measured as binary variable (indicating recurrent of detachment or not). Briefly, a 95% confidence interval around the proportion of retinal detachment in drug-treated subjects will be generated, and the primary endpoint will have been deemed to have been met if the upper bound of the confidence interval is lower than the weighted average historical control detachment rate. The primary efficacy analyses will be conducted on the ITT population with observed data only. Subjects who discontinue investigational treatment early will be encouraged to stay for any remaining safety assessments until the conclusion of the clinical trial. Subjects who have retinal detachment within 1-week post-operatively will be deemed to have failed Day 0 (day of surgery), and will be removed from the efficacy analysis.

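### Eyes removed for protocol violations or at the investigator's discretion before meeting the detachment criteria have no defined place in the observed-data primary analysis, and no endpoint follow-up is required for them

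*Combined protocol and SAP*

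**What the plan says.** Section 4.2 concerns leaving the trial, not only stopping injections. Its list begins "Subjects may be discontinued prior to their completion of the clinical trial due to" and includes "Protocol violations", "Any sound medical reason, as determined by the investigator" and a catch-all category (Others). Section 4.3 adds, without criteria: "Subjects may also be removed at the discretion of the principal investigator or at the wishes of the subject himself/herself".

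On analysis, section 9.1.1 states: "All data will be included, and no subjects will be excluded because of protocol violations". The one exception given there is detachment within the first post-operative week. Section 9.4.5 states: "The primary efficacy analyses will be conducted on the ITT population with observed data only". Section 9.4.2 adds: "No imputation method will be applied on recurrent retinal detachment data". Section 3.1 ties evaluability to completion: "For Part 1, approximately 100 evaluable eyes must complete the 24-week clinical trial".

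On follow-up, section 3.7 has subjects who stop product early complete the end-of-study visit when they stop. It also commits the sponsor and investigator to try to retain everyone to Week 24, and to follow early discontinuers for safety. Section 4.4 follows treated subjects over the scheduled course for safety. Section 9.4.5 encourages those who stop treatment to stay for the remaining safety assessments. By contrast, section 6.9 expressly follows subjects with a recurrent detachment that needs a return to the operating room through the Week 24 visit.

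**The concern.** Part 1b is open-label and single-arm. Success means that one upper confidence limit falls below a fixed historical rate, so no concurrent arm absorbs selective removal. The investigator who may remove a subject knows the treatment and examines the eye. Under section 6.8.4 the same person may also judge the endpoint if no separate evaluator is available.

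An eye that is getting worse but has not yet met the imaging criteria can be taken out of the trial. If its outcome is then missing, or is recorded as no event at an early-termination visit, the observed detachment rate falls. No intent is needed: it is enough that removal goes with poor prognosis. What is at stake is the false-success rate of the primary test.

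**Working it through.** **The plan's own figure.** The only sample-size calculation (section 9.3.1) belongs to the two-arm design that version 5.0 replaced: rates 0.2 and 0.5, 45 per group, two-sided 0.05, about 80% power. Without continuity correction:

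n = [1.96·√(2·0.35·0.65) + 0.8416·√(0.2·0.8 + 0.5·0.5)]² / 0.3² = 38.5, so 39 per group.

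With the correction: (38.5/4)·[1 + √(1 + 4/(38.5·0.3))]² = 44.9, so 45. The figure reproduces. There is no calculation for the single-arm test, so the rest rests on stated assumptions.

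**The rules side by side.** A subject removed for a violation remains in the ITT set by definition. If there was no event before removal, and no later endpoint assessment is required, there may be no Week 24 status to observe. Observed data only, with no imputation, then naturally means that the eye is not in the denominator. The other possibility is that the early-termination assessment (Table 1 labels Visit 16 as EOS/ET) is read as no event. No section chooses between the two. A detachment recorded before removal is observed and counts either way.

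**Inputs.**
- 100 eyes (section 3.1).
- Success rule: upper 95% limit below the historical rate p0 (section 9.4.5). The exact (Clopper-Pearson) limit is assumed, because the method is not named.
- p0 from 0.30 to 0.50: assumed, because no number is given.
- No drug effect: the true rate over all 100 eyes equals p0.
- r eyes removed, of which a share q would have failed: r = 5 or 10 and q = 0.5 or 0.8, all assumed.

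**If removed eyes leave the denominator.** With n = 100 − r:
- rate among kept eyes f = (100·p0 − r·q) / n
- c = the largest x for which the 0.975 quantile of Beta(x+1, n−x) is below p0
- false success = P[Binomial(n, f) ≤ c]

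Example: p0 = 0.40, r = 5, q = 0.8 gives f = (40 − 4)/95 = 0.379, c = 28, false success 5.5%. With f = 0.40 and the same 95 eyes it is 2.2%.

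| p0 | c (n=95) | Unbiased, n=95 | r=5, q=0.5 | r=5, q=0.8 | c (n=90) | Unbiased, n=90 | r=10, q=0.5 | r=10, q=0.8 |
|---|---|---|---|---|---|---|---|---|
| 0.30 | 19 | 1.9% | 3.2% | 6.4% | 18 | 2.2% | 6.0% | 19.7% |
| 0.35 | 23 | 1.6% | 2.4% | 4.8% | 22 | 2.1% | 4.4% | 15.0% |
| 0.40 | 28 | 2.2% | 2.8% | 5.5% | 26 | 1.9% | 3.1% | 11.2% |
| 0.45 | 32 | 1.6% | 1.9% | 3.8% | 30 | 1.6% | 2.1% | 8.1% |
| 0.50 | 37 | 2.0% | 2.0% | 4.0% | 35 | 2.2% | 2.2% | 8.4% |

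Over the five benchmarks the r=5, q=0.5 column spans 1.9-3.2%; at the two ends, 0.50 and 0.30, it is 2.0% and 3.2%. With all 100 eyes analysed and no removal, the rate is 2.5% at 0.40 and 2.1% at 0.35. At p0 = 0.50 and q = 0.5, removed eyes carry the average risk, so there is no bias.

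**If removed eyes are scored as non-events.** The denominator stays at 100, with limits c = 20, 25, 30, 34, 39 for p0 = 0.30, 0.35, 0.40, 0.45, 0.50. With q = 0.8, P[Binomial(100 − r, f) ≤ c] is 8.8-12.2% for r = 5 and 29.8-37.4% for r = 10. Treating all 100 eyes as binomial with the diluted rate p0 − r·q/100 gives 9.2-12.5% and 30.5-37.8%. Together: about 9-13% and 30-38%.

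**The case against.** The listed grounds are common protocol wording, and the plan has mitigating text. Section 4.2 requires each discontinuation and its reason to be reported to the sponsor and recorded. Section 3.7 commits to efforts at retention to Week 24. Section 4.4 follows treated subjects for safety, and dilated ophthalmoscopy is a safety endpoint, so a later detachment may well be seen. Section 6.8.4 collects imaging when the endpoint is met or at the conclusion of the trial, so a last status may exist. Section 9.4.9 also leaves the final procedures to the SAP, which could settle the scoring.

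Much of this stands: removed eyes need not vanish, and their later course may be known. But no section requires the endpoint visits after removal on these grounds, or says that later findings enter the primary analysis.

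The magnitude also depends on chosen inputs. With 5 eyes removed and half of them failing, false success stays close to the nominal one-sided 2.5%. That too is correct, and it is why a range is shown.

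Three stronger readings are tempting. A reader might infer that the plan deletes every removed subject; it does not say so, and events before removal count. A reader might infer that discretionary removal contradicts section 9.1.1; that sentence covers protocol violations only. A reader might take the drop-out of up to 20% in section 4.4 as the expected number of such removals; it is a total, in a section that also labels Week 1 detachments as dropped, and the share due to these grounds is not given.

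**Conclusion.** The gap is real and worth closing. Sections 4.2 and 4.3 allow an unmasked investigator to end trial participation on broad grounds. The primary analysis then uses observed data only, and the plan does not define how an eye removed without an event is scored.

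For protocol violations the conflict with section 9.1.1 is one of effect: the subject stays in the ITT set by name but may contribute no outcome. For discretionary and residual grounds it is the same missing-outcome bias without that contradiction.

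On the assumptions stated, the harm runs from negligible (few removals, ordinary risk) to serious: 8.1-19.7% false success if 10 eyes are dropped and 80% would have failed, and about 30-38% if those eyes are scored as non-events. The documents cannot place the trial within that range. They give neither the historical rate nor the number of removals expected, and nothing in them suggests that removals would be deliberate.

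**What to change.** In sections 4.2 and 4.3, for protocol violations, investigator discretion (including the medical-reason item where it amounts to discretion) and the residual category, separate stopping product from leaving the trial. For subjects who still consent, keep the scheduled endpoint imaging and evaluation visits through Week 24. State in section 9.4.5 that these outcomes enter the primary analysis. State there also how an eye with no Week 24 status is handled, and add a sensitivity analysis that counts such eyes as failures.

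Leave the existing clinical rules on injections, adverse events, pregnancy, endophthalmitis and no light perception as they are. A closed list of reasons to end follow-up would cut across those rules and is not needed.

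Cost: amendment wording, one added analysis, and a few subjects kept on visits already in the schedule.

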#### **4.3. Subject Withdrawal**

If intraoperative complete retinal reattachment is not achieved, subjects will not complete enrollment. These subjects will be dropped from enrollment and will be noted as screen failures.

Subjects who have retinal detachment within 1-week post-operatively will be deemed to have failed Day 0 (day of surgery) and will be removed from the efficacy analysis. These will be considered “dropped” subjects. Subjects receiving investigational product during this period will continue to be followed for safety.

Subjects will be removed from the clinical trial if they develop infectious endophthalmitis and/or no light perception vision.

Subjects may also be removed at the discretion of the principal investigator or at the wishes of the subject himself/herself.

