### **2.2.4. Safety Endpoints**

Safety endpoints analyzed in Part 1 and Part 2 include:

- BCVA at distance utilizing an ETDRS chart
- IOP
- Slit-lamp evaluation
- Dilated ophthalmoscopy
- Adverse event (AE) query (reported, elicited, and observed)

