#### **4.4. Handling of Subject Withdrawals or Subject Discontinuation of Clinical Trial Intervention**

Subjects that are dropped from the clinical trial prior to administration of the interventional investigational product or whom fail to achieve intraoperative complete retinal reattachment will be considered screen failures and will not be enrolled or included in analysis.

Subjects who have retinal detachment within 1-week post-operatively will be deemed to have failed Day 0 (day of surgery) and will be removed from the efficacy analysis. These will be considered “dropped” subjects.

Any subject receiving the investigational product will be followed for safety throughout the scheduled course of the clinical trial, or until the subject has reached a status of un-reachable.

It is anticipated that there will be a potential drop-out rate of up to 20%. To assure the clinical trial meets the required approximate 100 evaluable eyes for analysis, additional subjects may need to be enrolled to meet this goal.

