### **6.8.4. Endpoint Evaluation**

It is preferred that an evaluating investigator assess whether the primary endpoint has been met at the pre-specified evaluation timepoints Weeks 1 (V4), 4 (V7), 8 (V11), 12 (V13), 16 (V15), and 24 (V16). If an evaluating investigator is not available, the Treating Investigator may determine whether the primary endpoint has been met. The primary endpoint requires verification by the CRC before recurrent retinal detachment reoperation. In cases where CRC verification is not possible due to technical limitations with the Optical Coherence Tomography or fundus photograph, then the evaluating investigator will contact the trial medical monitor to confirm whether the primary endpoint has been met. Regardless, SD-OCT and wide-field imaging will be collected and verified by the CRC when the endpoint has been met, or at conclusion of the clinical trial, whichever is sooner.

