11. Silicone oil removal is required after Week 24.

Investigators will have discretion regarding the need for re-operation. Indications for re-operation may include endophthalmitis and recurrent retinal detachment, as defined in Section 3.6. Silicone oil cannot be removed within the 24-week trial period, unless for the above indications.

Recurrence of retinal detachment requiring a return to the operating room will prompt cessation of any further intravitreal injections and only Routine Surgical Care will be provided. Subjects will be followed through the Week 24 assessment visit.

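### Section 4.3 takes eyes with infectious endophthalmitis or no light perception out of the trial instead of only stopping injections, so scheduled imaging and endpoint evaluation to Week 24 are not required for them: a minor, cheaply avoided source of informative missing data

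*Combined protocol and SAP*

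**What the plan says.** Section 4.3 (Subject Withdrawal) sets a mandatory rule: "Subjects will be removed from the clinical trial if they develop infectious endophthalmitis and/or no light perception vision". The exit is from the trial, not only from study injections.

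Other sections bear on what happens next:

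- **Section 4.4**, on the handling of withdrawals, says: "Any subject receiving the investigational product will be followed for safety throughout the scheduled course of the clinical trial", or until the subject can no longer be reached.
- **Section 2.2.4** lists the safety endpoints as BCVA, IOP, slit lamp, dilated ophthalmoscopy and adverse events. Fundus photography and SD-OCT are not among them.
- **Section 6.9** stops injections after a re-detachment that needs surgery, and adds: "Subjects will be followed through the Week 24 assessment visit".
- **Section 6.8.4** places endpoint evaluation at Weeks 1, 4, 8, 12, 16 and 24. On images of both kinds (OCT and wide-field), it also says that they "will be collected and verified by the CRC when the endpoint has been met, or at conclusion of the clinical trial"; the earlier of the two applies.
- **Section 3.7** commits to efforts to retain everyone to Week 24, but also says: "Subjects who discontinue early from investigational product treatment will complete the end-of-study visit (Week 24) at time of discontinuation". It describes later contact with early discontinuers as being for safety.
- **Table 1 and Section 7.16** make Visit 16 both the Week 24 and the early-termination visit, with photographs, SD-OCT and endpoint evaluation.
- **Sections 9.4.2 and 9.4.5** rule out imputation of detachment data, run the primary analysis on observed data only, and encourage early discontinuers to stay for remaining safety assessments.

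**The concern.** The primary endpoint is a 24-week detachment status defined by imaging and verified by the reading center. Two serious ocular outcomes trigger an exit from the trial, so the data that go missing are linked to how badly the eye is doing. Infection is a listed risk of intravitreal injection (Section 1.3.1), and the regimen has 13 injections, so one of the two triggers can be a consequence of treatment.

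Section 6.9 already contains the better rule and applies it to re-detachment, but Section 4.3 does not use it. With observed data only and no imputation, the protocol does not say whether an eye that leaves without a detachment is dropped from the denominator or counted as event-free. At stake is the completeness of the primary proportion, whose upper 95% limit decides success. Part 1a control eyes matter for the secondary comparison of detachment rates.

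**Working it through.** **1. What remains required after removal under Section 4.3**

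| Item | Dosed eyes | Part 1a control eyes |
|---|---|---|
| BCVA, IOP, slit lamp, dilated ophthalmoscopy, adverse events | Yes, through Section 4.4 | No specific rule |
| Imaging and endpoint evaluation at exit | Plausible, through the early-termination visit | Plausible, through the same visit |
| Imaging if the endpoint is met later | Called for by Section 6.8.4, which does not say whether it covers removed subjects | Same |
| Scheduled photographs, SD-OCT and endpoint evaluation from exit to Week 24 | Not required | Not required |

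The gap is the last row for all removed eyes, plus the missing follow-up rule for controls. Section 3.7 may also bring the Week 24 visit forward to the time of exit. It is worded for stopping study drug, so applying it to these removals is an inference.

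**2. Evaluations missed**

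There are six endpoint evaluations. An eye that exits after the Week 1, 4, 8, 12 or 16 visit misses 5, 4, 3, 2 or 1 of them, always including Week 24.

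**3. How many eyes**

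The documents give no rate for either trigger. With 13 injections in each of 100 eyes there are 13 × 100 = 1,300 injections. At an assumed endophthalmitis risk of 0.02% to 0.1% per injection:

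- 1,300 × 0.0002 = 0.26 eyes
- 1,300 × 0.001 = 1.3 eyes

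The Poisson probability of three or more such eyes is about 0.2% at a mean of 0.26 and about 14% at a mean of 1.3. The no-light-perception count is unknown.

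**4. Effect on the primary proportion**

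The plan's only rate assumption is in Section 9.3.1: 0.2 versus 0.5 with 45 per group and about 80% power. That reproduces (80.1% with a continuity correction), but it belongs to the two-arm design used before Version 5.0. Here it only supplies a plausible rate. Assume 20 detachments in 100 eyes under full follow-up and Clopper-Pearson limits, since the plan does not name the interval method: 20/100 = 20.0%, upper limit 29.2%.

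| Removed eyes | Handling | All would have detached | None would have detached |
|---|---|---|---|
| 1 | Left out | 19/99 = 19.2% (upper 28.3%) | 20/99 = 20.2% (upper 29.5%) |
| 1 | Counted event-free | 19/100 = 19.0% (upper 28.1%) | 20/100 = 20.0% (upper 29.2%) |
| 3 | Left out | 17/97 = 17.5% (upper 26.6%) | 20/97 = 20.6% (upper 30.0%) |
| 3 | Counted event-free | 17/100 = 17.0% (upper 25.8%) | 20/100 = 20.0% (upper 29.2%) |

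Relative to 20.0%, one eye shifts the estimate by -1.0 to +0.2 points and three eyes by -3.0 to +0.6 points.

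**5. Could this change the conclusion?**

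The weighted historical rate is not stated. If it is near the 0.5 that the initial design assumed for standard of care, every upper limit above is well below it. A severe case is 20 detachments seen plus five removed eyes all counted as failures: 25/100, upper limit 34.7%, still below 0.5.

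**The case against.** The strongest reply is that dosed eyes are already largely protected. Section 4.4 directly follows Section 4.3, is headed as the handling of withdrawals, and covers every eye in the primary analysis, because that analysis uses drug-treated subjects only. Dilated ophthalmoscopy can reveal a detachment, Section 6.8.4 then calls for verified imaging, and the early-termination visit can document the retina at exit. This stands. A reader might infer from Section 4.3 that these eyes vanish and that their retinal status is irrecoverable. For dosed eyes the documents do not support that. The gap is confined to scheduled imaging and endpoint evaluation after exit.

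A reader might also infer a bias in favour of the drug large enough to matter. The larger possible shift is in that direction, but the sign depends on whether the removed eyes would have detached and on how they are counted. The three-eye extreme needs all three to have been destined to detach and all three to be counted as event-free.

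Two further points stand in part. Endophthalmitis is itself an indication for re-operation and permits early oil removal (Section 6.9), and in an eye without light perception it is unclear whether a detachment would require surgery, so later endpoint data may be hard to interpret. And observed-data analysis affects all dropouts, anticipated at up to 20%. The SAP to be finalised before database lock, which Section 9.4.9 makes the final authority on methods, may contain a classification rule; the supplied text does not include one. Neither point is a reason to remove these eyes by rule. Control eyes matter only for a secondary comparison, and allocation to that arm ended with Version 5.0.

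**Conclusion.** The point holds as a minor improvement. Section 4.3 creates avoidable, outcome-related missingness in scheduled imaging and endpoint evaluation. For dosed eyes it leaves safety follow-up, and probably an exit examination, in place. For removed Part 1a control eyes there is no specific follow-up rule.

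The likely size is about one eye or fewer from endophthalmitis, plus an unknown number with no light perception. That is -1.0 to +0.2 points for one eye, and it is unlikely to change the primary conclusion. These figures rest on an assumed endophthalmitis risk, an assumed 20/100 rate and an assumed interval method. The judgment on the conclusion also assumes a historical rate near 0.5, since the documents do not state one.

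**What to change.** - **Section 4.3:** replace removal from the trial with permanent discontinuation of study injections. Unless consent is withdrawn, subjects in either cohort continue the scheduled visits through Week 24, with endpoint evaluation and with imaging where the media allow.
- **Section 3.7:** state that the Week 24 visit is not brought forward for these subjects.
- **Section 9.4.5 and the SAP:** state that a removed or discontinued eye without a confirmed Week 24 status is not counted as event-free in the primary analysis. Add a sensitivity analysis that counts it as a failure. In the one-eye example where the removed eye would not have detached, this gives (20 + 1)/100 = 21.0%, upper limit 30.3%.

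The cost is wording in these places and a few extra visits for very few subjects. Some will have no vision in the study eye, or will have had the oil removed, and their endpoint status may be harder to interpret.
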